9.11 Data collection and handling

There will be a maximum of three questionnaires administered per participant: at Visit 1 (baseline; V1-D1 or V1-D1-SE), Visit 2 (Day 7; V2-D7) and Visit 3 (Day 60; V3-D60 or V3-D60-SE). All interviews will be documented on paper CRFs entered electronically, either centrally at the four sites, or at the clinics, into the OpenClinica eCRF/data base located at the LMU. Direct electronic data entry will be supported if a research site has the capacity to do that. The paper CRFs (V1-D1) will be retrieved from clinics on a weekly basis and stored at the central site or entered at the clinic. Data entry of V1-D1 will need to be entered within 6 days of enrolment as it is particularly critical to support the conduct of the V2-D7 phone calls.

V2-D7 and V3-D60 questionnaires will be administered mainly by phone by the research team, entered into the database and filed and stored centrally at the sites. For a subset of participants (approximately 50 per site) a more detailed socio-economic questionnaire (V1-D1-SE) will be conducted at baseline and at the last visit (V3-D60-SE). For those participants the Visit 3 questionnaire may be administered face-to-face.

In addition, details (study-ID, name, sex, age, date of enrolment) of each participant will be documented in a study register, which will stored in a secure location by the site until 10 years after the end of the study unless local regulations or institutional policies require a longer retention period. The study register will be compared with the TB registers and clinic records to ascertain diagnostic results (such as smear results in the standard of care clinics), TB registration number and TB initiation dates. This will be documented on the study TB outcome worksheet. The completed worksheet will be retrieved at the end of the study, entered electronically and stored centrally.

Data on number of contact attempts, contact information provided by trusted proxy, date and location of home visits will be documented on paper in free text. This information will not be entered and stored centrally.

All paper forms (including consent form) will be stored in secure and locked cupboards with only authorised person having access to the forms. The electronic database will not include any names, but only study numbers. The OpenClinica Enterprise version 4.0 database will be secure, password protected and regularly backed-up. Only authorised people will have access to the database.

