12.1 Visit 1 Baseline visit

Patients presenting with symptoms suggestive of pulmonary TB to one of the study clinics will be invited to be screened for inclusion in the study. Before any study-specific screening procedures will be performed, all patients will sign and date (or thumbprint) the latest version of the ICF. Illiterate participants will be encouraged to have a witness present.

After informed consent has been obtained, the patient will receive a study number. The ICF will be labelled with the study number. A primary health care nurse or dedicated researcher staff will administer a questionnaire (V1-D1) and ask the patient about their contact details and the contact details of a trusted proxy (locator form). In addition, 5 to 10% participants per site will be invited to answer a socio-economic questionnaire about income, cost of care seeking, productivity losses, diagnostics and treatment (V1-D1-SE). For these participants a face-to-face interview may be conducted.

Depending on the clinic, the patient will receive a diagnostic work-up according to the national algorithm (smear microscopy and/or off-site Xpert testing) or the study intervention (Truenat

Protocol short title: TB-CAPT CORE Truenat trial

Protocol Number: TB041-3/1 -MZ

Protocol Version: 4.0 - CONFIDENTIAL - Page 40 of 57

platform/TB assays on site). Further diagnostic investigations and TB treatment initiation will be as clinically indicated. All clinical care and further investigations will be provided within the governmental health care service. Patient details (including name, sex, age, and study-ID) will be documented in a study register, which will remain at the clinic. All patients will receive a study card with their details (including name, sex, age and study number and enrolment date) to take home with them. They will be asked to show the card if they present to the clinic again.

12.2 Visit 2: Day 7

All participants will be called by telephone 7 days after enrolment (between day 8 and day 21 after enrolment). Three attempts will be made to contact a participant by phone. If these attempts are unsuccessful the trusted proxy will be contacted to find out about the participant's whereabouts and arrange for a return call by the participants or a home visit. A home visit will be conducted for those participants who cannot be reached by phone.

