13.6 Other analyses

Other analysis will include

- i) comparison of proportions using similar methodology as for proportion-related endpoints:
 - initiating TB treatment with microbiologically diagnosed (or all) TB at 60
- ii) time to TB treatment initiation (adjusted for strata) across arms
 - for microbiologically confirmed TB cases
 - for clinical diagnosed TB case
 - for all TB cases

Analysis of cost, number of health care visits and symptoms will be done either by comparing proportions or mean (adjusted for strata).

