 - 1. Participants diagnosed with TB either clinically or with microbiological confirmation
 - 2. Participants clinically diagnosed with TB
 - 3. Participants with microbiological confirmation of TB

The endpoint of interest is a binary outcome of successful treatment outcome "yes" or "no" among patients allowing us to calculate the proportions for each of the groups described.

The hypotheses of interest are:

H0: Number of treatment successes in intervention arm is same as in the SOC arm vs.

 ${\it H1:Number\ of\ treatment\ successes}$ in intervention arm is different from the SOC arm And.

H0: Proportion of treatment success in intervention arm is same as in the SOC arm vs.

H1: Proportion of treatment success in intervention arm is different from the SOC arm

This is translated in terms of odds ratio (OR) for the odds of successful treatment in the intervention arm is significantly different from the SOC arm leading to the hypothesis:

 $H0: OR_{Intervention:SOC} = 1 \ vs. \ H1: OR_{Intervention:SOC} \neq 1$

The number of participants with a successful treatment in described conditions will not be subject to a formal statistical hypothesis test.

Morbidity related endpoints:

Prevalence of current cough, limited appetite, weakness at 60 days from enrolment

QMS Form number: FM-06-02-	CONFIDENTIAL	Page 9 of 26
05/v2.0		

FIND >>>	Statistical Analysis Plan		
Protocol number:	TB041-3/1-TAN / -MOZ		
Document version:	5.0	Document date:	11-JUL-2023

The endpoint of interest is a binary outcome of physical symptoms such as current cough, limited appetite or weakness at 60 days from enrolment "yes" or "no" among patients allowing us to calculate the proportions for each of the groups described.

H0: Proportion of physical symptoms in intervention arm is same as in the SOC arm vs.

H1: Proportion of physical symptoms in intervention arm is different from the SOC arm

This is translated in terms of odds ratio (OR) for the odds of physical symptoms in the intervention arm to be different from the SOC arm leading to the hypothesis:

 $H0: OR_{Intervention:SOC} = 1 \text{ vs. } H1: OR_{Intervention:SOC} \neq 1$

Direct cost and productivity related endpoints:

· Patients' costs related to care

The endpoint of interest is a continuous outcome of patient costs related to care

H0: Mean cost in intervention arm is same as in the SOC arm vs.

 $\mathit{H1}: \mathit{Mean\ cost}\ in\ intervention\ arm\ is\ different\ from\ the\ SOC\ arm$

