4.3 Analysis of the secondary outcomes

Diagnosis, treatment, and morbidity related endpoints

The analysis of the binary outcomes will be performed in the same way as the analysis of primary outcomes using GLMMs with Poisson or binomial distributions, for count or proportion data respectively.

Time-to-event analyses will be performed using mixed-effect Cox proportional hazards (PH) regression models (*coxme* package, *coxme* function in R). Kaplan Meier curves will be used to graphically represent the data. The possibility of non-proportional hazards will be assessed using Schoenfeld individual test and its graphical representation.

In case of non-proportional hazards, we will consider to split the time, use an interaction term, use a complementary log-log generalized linear model, or a combination of these approaches. If non-proportional hazard is caused by a confounder, we may set that variable as a strata.

As for primary outcome, the models will be adjusted for gender, age, HIV status, country, and asset index that is described below. In case of necessity, the models may be adjusted for the setting (i.e. urban, rural, peri-rural nesting the clusters), and site.

Direct cost and productivity, modelled cost, and cost effectiveness related endpoints:

MSeveral of these endpoints are not estimated using standard statistical analyses, but rather reflect descriptive analyses or model-based analyses that are not purely statistical in nature.

Patients' costs related to care

Patient costs will be estimated as the mean cost per patient interviewed. These costs will include direct and indirect costs incurred because of TB diagnosis. Direct costs will include all medical (including consultation fees and any out-of- pocket payment for medicines, X-rays, and diagnostics) and non-medical expenses (including travel costs of participants and caregivers,

QMS Form number: FM-06-02-	CONFIDENTIAL	Page 15 of 26
05/v2.0		_

FIND >>>	Statistical Analysis Plan		
Protocol number:	TB041-3/1-TAN / -MOZ		
Document version:	5.0	Document date:	11-JUL-2023

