food costs incurred while in hospital, money spent buying any special foods). Indirect costs will be estimated as the opportunity cost of time spent seeking care (from the time of symptom onset to the time of treatment initiation), plus any lost productivity due to illness. Additional information from the scientific literature will be used to estimate costs that are not directly estimated (e.g., hospitalization costs, costs of TB treatment).

The total cost for each patient will be estimated as the sum of direct and indirect costs, and the mean cost will be taken as the sum of these total costs, divided by the number of patients.

Number of lost working days

We will use patient interviews to record the self-reported number of working days lost due to TB illness in both arms. This will be directly estimated; no additional statistical methods will be used. 95% confidence intervals will be calculated assuming a Poisson distribution.

Monthly earnings

To estimate loss in income, we will record the number of missed working days or missed working hours owing to TB illness, from the time of symptom onset to the time of treatment initiation. This number of days/hours will be multiplied by the average daily/hourly wage of employed laborers in each country to estimate the monthly earnings lost as a result of seeking care. If the patient does not have formal employment but works informally, e.g., as an agricultural worker, we will use their self-reported reduction in productivity (as a percentage of total productivity) over the course of the past year. This number will be multiplied by the average agricultural wage/earnings in each country and reported on a monthly basis. We will then calculate the mean monthly earnings lost as the sum of lost income (as described above), divided by the number of participants from which those data are obtained.

• Unit costs of diagnosis and treatment, modified societal perspective

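### SAP 4.3 gives only raw means for the patient cost and lost working days that SAP 2.2 tests between arms: no stratum term (required for cost by Protocol 13.6), no stated clinic effect, no use of Visit 1 cost

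*SAP*

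**What the plan says.** **Hypothesis.** SAP 2.2 states the null for patient cost as "Mean cost in intervention arm is same as in the SOC arm" and expresses it as a mean difference of zero. Lost working days gets the same form. Unit costs and the cost-effectiveness ratio are exempted from formal testing there; these two endpoints are not.

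**Estimator.** SAP 4.3 adds direct and indirect cost for each patient, and then "the mean cost will be taken as the sum of these total costs, divided by the number of patients". No between-arm model or interval is named for patient cost. Lost working days is to be estimated directly, with a Poisson interval and no further method.

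**Protocol rule.** Protocol 13.6: "Analysis of cost, number of health care visits and symptoms will be done either by comparing proportions or mean (adjusted for strata").

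**Cost window.** The time component of indirect cost is the "opportunity cost of time spent seeking care (from the time of symptom onset to the time of treatment initiation"). For cost as a whole the text is looser: "These costs will include direct and indirect costs incurred because of TB diagnosis". Direct cost has no start date, and the lost-days paragraph gives no window.

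**Data.** Protocol 12.1 describes the baseline instrument as a "socio-economic questionnaire about income, cost of care seeking, productivity losses, diagnostics and treatment (V1-D1-SE"). Protocol 9.11 says that for a subset "a more detailed socio-economic questionnaire (V1-D1-SE) will be conducted at baseline and at the last visit (V3-D60-SE"). Protocol Table 1 lists V1-D1-SE as the only source for the cost endpoint.

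**The concern.** A formal comparison is announced, but no method is given that respects how the clinics were allocated. The strata (site and clinic size) were used in the randomisation, and clinics are the randomised units. A test that ignores clinics can overstate precision, and one that ignores strata departs from the protocol.

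The outcome also contains cost that arose before enrolment, where the intervention cannot act; this is explicit for care-seeking time. Visit 1 asks about care-seeking cost and, in the extended questionnaire, loss of income. A baseline covariate is therefore planned data that the analysis leaves unused.

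The cost subset is small, and patient cost feeds the unit-cost and cost-effectiveness results, which SAP 4.3 analyses by country.

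**Working it through.** **Plan's own figure.** There is none. The plan sizes only the primary endpoint, and gives no cost SD, intracluster correlation (ICC), baseline correlation or pre-enrolment share. Every value of these below is an assumption.

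**Size of the cost subset.** Protocol 9.11: about 50 × 4 sites = 200, or 200/28 = 7.1 per clinic. Protocol 9.8: 5–10% of 4200 = 210 to 420, up to 420/28 = 15 per clinic.

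**1. Clinic effect.** If respondents are treated as independent, the standard error (SE) is too small by √(1 + (m − 1) × ICC).
- m = 7: ICC 0.02 gives √1.12 = 1.06; ICC 0.05 gives √1.30 = 1.14.
- m = 15: √1.28 = 1.13 and √1.70 = 1.30.

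A Poisson interval also fixes the variance at the mean, so it is too narrow by a further factor if lost days vary more than that.

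**2. Does pre-enrolment cost shift the mean difference?** Write total = pre + post. The expected arm difference in total is the difference in pre plus the difference in post. If pre has the same mean in both arms, it cancels.

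Simulation: 28 clinics in 7 strata of 4, 7 respondents per clinic, skewed costs, mean total 100, post-enrolment cost cut by 30%, 4000 runs. The adjusted analysis uses pre-enrolment cost and strata.

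| Pre-enrolment share of mean cost | True difference | Raw mean estimate | SE raw | SE adjusted |
|---|---|---|---|---|
| 25% | −22.5 | −22.6 | 14.3 | 12.3 |
| 50% | −15.0 | −14.9 | 14.0 | 8.2 |
| 75% | −7.5 | −7.1 | 15.6 | 3.9 |

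The raw difference is on target and the cost is in precision. Only the relative reduction shrinks (30% becomes 22.5%, 15% and 7.5%), and the SAP does not use it. Strata alone left both estimate and SE unchanged, because each stratum was split 2:2 with equal numbers per clinic; with unequal numbers the estimate would change.

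**3. If the arms differ before enrolment.** At a 50% share, mean pre-enrolment cost is 50, so a 20% arm difference is 10. The raw expectation moves from −15 to −15 + 10 = −5 or −15 − 10 = −25 (simulated −5.1 and −25.0). The adjusted estimate stays at −15.2 and −14.4.

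**4. Gain by share of variance.** Adjustment multiplies the SE by √(1 − ρ²). If pre and post are independent, ρ² is the pre-enrolment share of total-cost variance. A separate simulation used 28 clinics, 7 per clinic, ICC 0.05, 1500 runs, an effect chosen for about 80% unadjusted power, and clinic-mean analyses without and with pre-enrolment cost:

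| Share of variance | Power, unadjusted | Power, adjusted |
|---|---|---|
| 10% | 80.5% | 82.1% |
| 25% | 79.1% | 87.5% |
| 50% | 77.3% | 96.7% |

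At 50% the SE fell from 0.168 to 0.121 SD; the formula gives 0.168 × √0.5 = 0.119.

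**5. Detectable difference.** With 100 per arm and clustering ignored, (1.96 + 0.84) × √(2/100) = 0.40 SD at 80% power. At ρ = 0.5 this becomes 0.40 × 0.866 = 0.34 SD, and at ρ = 0.7, 0.40 × 0.714 = 0.28 SD (from unrounded values).

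**The case against.** The best case for the plan runs as follows. The protocol's stratum rule applies whether or not the SAP repeats it. SAP 4.1 says that clusters are handled by a random intercept. SAP 4.3 calls several of these endpoints descriptive or model-based. The allocation is restricted by site and clinic size, which limits chance imbalance on those factors.

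Part of this stands: the omission may be a failure of cross-reference. But SAP 4.1 ties the random intercept to generalised linear and proportional hazards models and says nothing about strata. The covariate-adjusted models in SAP 4.3 are listed for diagnosis, treatment and morbidity endpoints. And SAP 2.2 keeps a formal hypothesis on both quantities.

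A reader might infer that pre-enrolment cost dilutes the estimated effect. The documents do not support that: the effect measure is an absolute mean difference, and unaffected cost cancels from it in expectation. Nor do they show that the arms differ in pre-enrolment cost. Unblinded clinics, and the SAP's own remark in section 8 that recruitment may run faster in intervention clinics, make a difference possible, not established. A reader might also take all cost to run from symptom onset; the SAP says so only for care-seeking time and the earnings calculation.

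Two objections limit the remedy. If Table 1 is right and V1-D1-SE is the only cost source, the baseline value is the endpoint, and adjusting for it would be circular. And V1-D1-SE also covers diagnostics and treatment, while the Visit 1 window in the schedule of events extends to 48 hours after clinics are already allocated. Adjusting for the whole form could therefore remove part of the effect.

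**Conclusion.** The gap is real. Two tested secondary endpoints have a descriptive estimator and no comparative model. For patient cost, the stratum adjustment in Protocol 13.6 is missing from SAP 4.3. Protocol 13.6 does not name lost working days, but the same allocation argument applies. This part rests on the text alone.

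The case for baseline adjustment is about precision and protection against imbalance. It does not correct a known bias. Its size depends on the unknown share of cost variance that precedes enrolment: about 2 points of power at 10%, about 8 at 25% and about 19 at 50%, assuming independent pre- and post-enrolment cost, 7 respondents per clinic and ICC 0.05. It also assumes that follow-up cost is actually collected at Day 60, on which Table 1 and Protocol 9.11 disagree.

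**What to change.** 1. Reconcile Protocol Table 1 with Protocol 9.11, and state which questionnaire supplies follow-up cost. State the window for direct cost and for lost working days.
2. In SAP 4.3, estimate the arm difference in patient cost and in lost working days with arm and randomisation stratum as fixed effects and clinic as random intercept. Give a clinic-level bootstrap interval, replacing the Poisson interval for lost days. This applies however step 1 is settled.
3. If follow-up cost comes from V3-D60-SE, add the participant's pre-enrolment cost from V1-D1-SE as a covariate. Restrict it to items incurred before the enrolment visit, so that no Visit 1 testing or treatment cost is adjusted away.
4. Keep raw means by arm as description, and carry the adjusted difference into the incremental cost.

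The cost is SAP wording and modest extra analysis. Step 2 needs no new data; step 3 needs none provided both questionnaires record the relevant cost items. The one small burden is a stated handling for participants with no usable baseline value, such as a missing-baseline indicator.

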This is translated in terms of a mean difference (MD), comparing the intervention arm to the SOC arm.

 $H0: MD_{(int-SOC)} = 0 \text{ vs. } H1: MD_{(int-SOC)} \neq 0.$

Number of lost working days

The endpoint of interest is a continuous outcome.

H0: Mean lost working days in intervention arm is same as in the SOC arm vs.

H1: Mean lost working days in intervention arm is different from the SOC arm

This is translated in terms of a mean difference (MD), comparing the intervention arm to the SOC arm.

 $H0: MD_{(int-SOC)} = 0 \text{ vs. } H1: MD_{(int-SOC)} \neq 0.$

· Monthly earning

The endpoint is a continuous outcome.

H0: Mean monthly earning in intervention arm is same as in the SOC arm vs.

H1: Mean monthly earning in intervention arm is different from the SOC arm

QMS Form number: FM-06-02-	CONFIDENTIAL	Page 10 of 26
05/v2.0		-

FIND >>>	Statistical Analysis Plan		
Protocol number:	TB041-3/1-TAN / -MOZ		
Document version:	5.0	Document date:	11-JUL-2023

This is translated in terms of a mean difference (MD), comparing the intervention arm to the SOC arm.

 $H0: MD_{(int-SOC)} = 0 \text{ vs. } H1: MD_{(int-SOC)} \neq 0.$

Modeled cost and cost-effectiveness endpoints:

Unit costs of diagnosis and treatment, modified societal perspective

The endpoint will be calculated from measured costs from the patient and health system perspectives.

The primary outcome will be the sum of patient plus health system costs, expressed as unit costs (e.g., cost per test, cost per TB treatment), under the intervention and under the standard of care.

This outcome will not be subject to a formal statistical hypothesis test.

Incremental cost-effectiveness ratio, modified societal perspective

The endpoint will be calculated from cost and effectiveness outcomes, including both patient and health system perspectives.

The primary outcome will be the incremental cost per patient treated for TB, comparing the intervention to the standard of care.

This outcome will not be subject to a formal statistical hypothesis test, however the components that make up the outcome are.

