4.1 General approach

All analyses will be performed on the MITT and PP populations. Because there was a protocol deviation (i.e. participants with missing V2 or V3), the potential difference in the primary outcome between the two populations will be explored as described in *Section 7.0*.

All analyses (i.e. generalized linear models and proportional hazards models) will take into account the effect of the clusters using a mixed model approach, introducing a random intercept for each cluster. Details of the models for each outcome are given in the sections below.

For all statistical tests, alpha will be set to 0.05 for rejecting the null hypothesis. Since multiple comparisons will be performed, p-values will be adjusted using Benjamini-Hochberg method.

The proportion of observations with missing values will be summarised for all outcome variables. Missing and invalid data will not be imputed. Baseline measures will be reported for individuals with missing data on an outcome of interest, including those who withdraw or are lost to follow-up. For each analysis, the baseline measures (demographic and laboratory data) will be compared between participants with complete and incomplete data using T-Tests or Chi² tests, for continuous or categorical variables respectively.

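### The Poisson interval prescribed for lost working days is likely too narrow, mainly because it ignores variation between people

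*SAP*

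**What the plan says.** SAP 4.3 describes the data for this endpoint as follows: "We will use patient interviews to record the self-reported number of working days lost due to TB illness in both arms". On method it says: "This will be directly estimated; no additional statistical methods will be used". The interval rule comes next: "95% confidence intervals will be calculated assuming a Poisson distribution". No clinic effect, stratum, overdispersion term or robust variance is named.

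SAP 2.2 describes the same endpoint differently. It states that "The endpoint of interest is a continuous outcome" and sets a two-sided hypothesis on the arm means, with the alternative "Mean lost working days in intervention arm is different from the SOC arm", expressed as a mean difference. No test procedure for that hypothesis appears in 4.3.

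SAP 4.1 has a general rule: "All analyses (i.e. generalized linear models and proportional hazards models) will take into account the effect of the clusters using a mixed model approach". SAP 1.1 identifies the cluster with the clinic, which is the unit of randomisation.

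**The concern.** A Poisson interval is right for a count of independent events. Lost working days are not that: one illness produces a run of days, some people lose none and others lose many. The variance between people can therefore exceed the mean, and the Poisson standard error cannot reflect this. Respondents are also grouped in randomised clinics, which adds variance that the rule omits.

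At stake is the meaning of the 95% label on the lost-days estimates. If the Poisson standard error is also carried into the mean-difference test of SAP 2.2, that test would reject too often. Point estimates are unaffected.

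**Working it through.** **1. Inputs.** The documents give no precision figure for this endpoint, so there is no stated result to reproduce. They also give no mean, SD, share of zeros or clinic-level variation for lost days. What can be taken from them:
- Clinics: 28, with 4200 participants (SAP 8).
- Respondents: productivity losses are collected on the extended socio-economic questionnaire (SAP 3.1). I take lost days to come from there. Protocol 9.11 gives about 50 per site: 50 × 4 = 200, and 200/28 = 7.14 per clinic. SAP 3.1 gives 5–10%: 210 to 420, or 7.5 to 15 per clinic.
- Between-clinic CV: 0.25. SAP 8 gives this for the primary endpoint only, as a within-pair default. It is borrowed here as an assumption.

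Assumed: mean 1 to 20 days, and person-level (within-clinic) SD as a multiple of the mean.

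**2. Formula.** With m respondents per clinic and n per arm, the Poisson variance of an arm mean is mean/n. The variance allowing for people and clinics is (SD² + m·CV²·mean²)/n. The ratio of standard errors is therefore

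r = √(SD²/mean + m·CV²·mean).

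It is the same for one arm mean and for the difference between two equal arms. Approximate coverage of the nominal 95% interval is 2Φ(1.96/r) − 1.

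**3. Results with SD = mean.** Person-level variation alone gives r = √mean. The clinic term multiplies this by √(1 + 7.14 × 0.0625) = √1.446 = 1.20. Coverage was simulated with 14 clinics per arm, 7 respondents each and 4000 replicates.

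| Mean (days) | r, people only | r, people and clinics | Simulated coverage |
|---|---|---|---|
| 1 | 1.0 | 1.2 | not simulated |
| 2 | 1.4 | 1.7 | 75% |
| 5 | 2.2 | 2.7 | 53% |
| 10 | 3.2 | 3.8 | 40% |
| 20 | 4.5 | 5.4 | 28% |

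At a mean of 1 day, SD = mean is exactly Poisson variance, so the factor of 1.2 is all clinic effect. From 2 days upward, person-level variation is the larger part.

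**4. Clustering on its own.** Once person-level variance is handled, ignoring clinics understates the standard error by √(1 + (m − 1)·ICC). For an assumed ICC of 0.01 to 0.10 this is:
- m = 7.14: √1.061 = 1.03 to √1.614 = 1.27
- m = 15: √1.14 = 1.07 to √2.40 = 1.55

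**5. Other SDs** (m = 7.14, CV 0.25, means 1, 2, 5, 10, 20):
- SD = 2 × mean: 2.1, 3.0, 4.7, 6.7, 9.4
- SD = 0.5 × mean: 0.8, 1.2, 1.9, 2.6, 3.7

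The interval stops being too narrow only for short absences with unusually little spread.

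**6. Zeros.** Protocol 13.8 assumes TB prevalence of 12% to 20% among those enrolled, and the SAP item counts days lost to TB illness. As an illustration, suppose participants without TB report zero, and those with TB report a Poisson count with mean D, with no clinic effect. Then variance/mean = 1 + D(1 − prevalence). At D = 10 this is 1 + 10 × 0.88 = 9.8 to 1 + 10 × 0.80 = 9.0, so r = 3.1 to 3.0. The overall mean would be only 1.2 to 2.0 days. A low mean therefore does not by itself make the Poisson interval safe.

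**The case against.** The strongest reply is that the size cannot be known. Every factor above depends on a mean, an SD and a clinic variation that the plan does not state. This stands. A reader might infer that the interval is certain to be several times too narrow; the documents do not support that, and at means of 1 to 2 days with SD equal to the mean the factor is only 1.2 to 1.7.

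Three other strong readings are tempting and fail:
- **The missing clinic effect is the main cause.** With 7 to 15 respondents per clinic it is the smaller part unless absences are short and little dispersed.
- **SAP 4.3 flatly contradicts SAP 4.1.** The rule in 4.1 is glossed as covering generalized linear and proportional hazards models, and 4.3 names neither for this endpoint. The text leaves a gap rather than a clear contradiction. The firmer mismatch is with 2.2.
- **The error carries into indirect costs.** SAP 4.3 builds patient costs from per-patient totals and lost earnings from days or hours times a wage. Cost-effectiveness uncertainty uses the empirical distribution of unit costs. The Poisson interval enters none of these.

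It can also be said that SAP 4.3 calls several of these endpoints descriptive. But SAP 2.2 expressly exempts unit costs and the cost-effectiveness ratio from formal testing and does not exempt lost days. A descriptive interval labelled 95% should in any case cover about 95%.

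Finally, the stakes are modest, and this stands. SAP 1.2 treats cost and productivity endpoints as operational, and the protocol's endpoint lists name only patient costs under that heading. No primary, diagnostic or treatment conclusion depends on this interval.

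**Conclusion.** The rule is wrong as written, rather than merely short of detail. It fixes variance equal to mean, without a clinic term, for an endpoint that the same SAP calls continuous and compares by a mean difference between arms randomised by clinic. Followed literally, it gives intervals that are too narrow whenever the variance between people exceeds the mean, and clustering adds to this.

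The direction is likely and the size is conditional: the working's figures rest on SD equal to the mean, 7 respondents per clinic and a borrowed clinic CV of 0.25. More zeros or long absences would enlarge the shortfall; absences with little spread would shrink or remove it. An inflated false-positive rate follows only if the unnamed test in 2.2 uses the Poisson standard error. This is worth correcting for a secondary productivity endpoint and does not touch the main results.

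**What to change.** In SAP 4.3, delete "This will be directly estimated; no additional statistical methods will be used" and the Poisson sentence after it. In their place, report the arm means and their difference with a bootstrap interval that resamples whole clinics within arm. A cluster-level comparison of means, or a negative-binomial mixed model with arm and a clinic random intercept, would also serve. State that the same method gives the mean-difference test in SAP 2.2, so that estimate, interval and test agree.

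The cost is one SAP paragraph and one analysis step, with no new data. The downside is a wider interval.
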